3. STUDY PROCEDURES

Data Collection

All study participants will complete objective weight measurements, two dietary recalls, and self-administered online surveys at baseline and 6 months (post-intervention). At 3 months, only psychosocial measures and medical events will be collected via online survey and telephone. Participants will receive \$50, \$25, and \$75 for completing baseline, 3, and 6-month assessments, respectively. Online surveys will include measures of theoretical mediators, other psychosocial constructs, and process measures. We will send emails and texts prompting participants to complete assessments, with follow-up emails and phone calls to non-respondents, as necessary. Measures and timing are described below.

Measures

Where possible, we are measuring constructs using validated and recommended scales from the ADOPT Core Measures Project ⁵⁸⁻⁶⁰ (indicated below with ACM), an NIH-supported initiative to permit collaboration, pooling across obesity interventions, and to search for predictors of heterogeneity in response to treatment.

Primary outcome (Weight): Weight will be objectively measured at the participant's home at all time points. We will instruct participants to weigh themselves in light clothing, without shoes, on the wireless scales at each assessment time point. The participant will weigh themselves 3 times in succession to indicate the assessment weight on the date requested. A subset of participants local to our facilities (up to n=40) will be invited at baseline to complete in-person weight measurements to further validate smart scale weights with clinic weight.

Other Anthropometric and Key Behavioral Mediators (collected at baseline, 3 months, and 6 months)

- **Height (Baseline only):** Participants will self-report height using an item from the Behavioral Risk Factor Surveillance System (BRFSS), ⁶¹ adapted for the Health Information and National Trends Survey. ⁶²
- **Dietary Intake (Baseline, 6 months):** Changes in dietary intake will be assessed using the NCIs Automated Self-Administered 24-hour Recall (ASA-24). Participants will complete two self-reported recalls; one weekday and one weekend day. The 24 recall is a validated method of measuring diet. ⁶³ Using two recalls permits adjustment of estimates for intraindividual variation and is superior to administering one recall.

- Self-reported Physical Activity (ACM). Physical activity will be assessed with the Paffenbarger Physical Activity Questionnaire (PAQ)⁵⁶ which assesses leisure-time activity. The PAQ provides an estimate of minutes per week of moderate-to-vigorous intensity, and calories/week of light (5 kcal/min), medium (7.5 kcal/min), and high (10 kcal/min) intensity activities. PAQ changes have been predictive of weight change.
- Sedentary Activity (ACM). Given the increasing recognition of the effects of sedentary activity independent of physical activity, we will use the Sedentary Behavior Questionnaire from CARDIA/EARLY trials.⁶⁴

Proposed Theoretical Mediators (collected at baseline, 3, and 6 months)

- Autonomy Support (3 and 6 months only). We will adapt items from the Health Care Climate Questionnaire, which is a measure of how the participant perceives support from a healthcare provider, to measure autonomy support from the program.⁶⁵ The scale includes 15 items rated on a scale of 1 (*strongly disagree*) to 7 (*strongly agree*) (e.g., “I feel that [the program] has provided me choices and options.”)
- Competence for Diet and Physical Activity (ACM). The Perceived Competence for Scale includes 4 items that measure perceived competence for diet and 4 items for physical activity.⁶⁶ Items are rated on a 7-point of 1 (*not at all true*) to 7 (*very true*) (e.g., “I feel confident in my ability to maintain a healthy diet.”)
- Relatedness (3 and 6 months only). Relatedness will be measured with 3 items adapted from the 8-item Relatedness subscale of the Basic Need Satisfaction at Work Scale.^{49,67} Examples include “The messages demonstrate caring about me as a person” and are scored on a Likert scale from 1 (*strongly disagree*) to 7 (*strongly agree*).
- Message Relevance (3 and 6 months only). Perceived message relevance will be measured with two items used in our previous work⁶⁸ and adapted from previous studies of tailored messages.^{45,69} Participants were asked to rate how strongly they disagree or agree with the statements about messages being “written personally for me” and “applied to my life.” Responses are on a 5-point scale from 1 (*strongly disagree*) to 5 (*strongly agree*).
- Treatment Self-Regulation (ACM). The Treatment Self-Regulation Questionnaire (TSRQ) will be used to assess autonomous and controlled motivation for making changes in diet (15 items) and physical activity (15 items).⁷⁰ Examples item: “Because I feel that I want to take responsibility for my own health” answered on a scale of 1 (*not at all true*) to 7 (*very true*).

Other Psychosocial and Behavioral Measures (collected at baseline, 3, and 6 months)

- Quality of Life. All participants will complete the CDC Health-Related Quality of Life measure (referred to as “Healthy Days Measures”).¹³⁶ This 4-item questionnaire reliable, valid, and responsive to change.
- Depression (ACM). Depressive symptoms have been associated with changes in weight, diet, and physical activity and will be assessed with the Center for Epidemiological Studies Depression Scale (CES-D).¹³⁷
- Weight Control Strategies (ACM). Participants will be asked about frequency of use of 20 weight control strategies such as “ate only when I was hungry” with a scale used in the EARLY trials.¹³⁸
- Hunger, Restraint, Disinhibition. The Three Factor Eating Questionnaire (TFEQ) is a 51-item self-report instrument assessing three factors of dietary restraint, disinhibition and hunger.¹³⁹
- Perceived Stress (ACM). The Perceived Stress Scale is a 10-item measure that assesses stressful situations in the last month.¹⁴⁰
- Binge Eating (ACM). Participants will complete the revised Questionnaire on Eating and Weight Patterns (QEWP-5) to assess frequency of binge eating, loss of control, and compensatory behaviors.¹⁴¹

Process and Adherence Measures (collected over 6 months)

- Dietary Monitoring. Objective self-monitoring of dietary intake will be assessed using data from the smartphone application food log (for simplified conditions) and Fitbit food log (for calorie conditions).
- PA monitoring. Objective self-monitoring of PA will be assessed via the Fitbit tracker data. Using the Fitbit API, the study will collect data on the number of days the Fitbit was worn (steps $\geq 500/\text{day}$).⁹⁵
- Self-weighing. Self-weighing habits will be objectively measured via the smart scales to calculate percent of days weighed, and average self-weighing days per week.

- Other Engagement Measures. We will examine app views as mean, median, and monthly percentage, to account for the skewing of app data. App views are similar to website logins, which have been associated with weight loss.^{48,50,82,83} We will examine number of lessons accessed and feedback messages viewed.
- Program Acceptability and Satisfaction. Participants will complete a post-treatment program evaluation about intervention perceptions and experiences, using questions from our previous studies.

Other Measures (collected at baseline, 3, and 6 months, unless otherwise indicated)

- Medical events and symptoms will be collected at 3 and 6 months in a scheduled telephone call. Responses will be reviewed to determine if a Serious Adverse Events form is required.
- Demographics. At baseline, standard demographic information will be collected
- Medical history, Medication use. Self-report of both prescription and non-prescription medications.
- Smoking, alcohol use. Smoking and alcohol use will be assessed at each time point.

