Adaptive Activity Goals. Participants will be randomized to receive weekly adaptive or daily adaptive daily physical activity goals. In the weekly adaptive group, participants will receive a new daily activity goal at the beginning of each program week and the daily goal remains constant throughout the week. In the daily adaptive group, participants will receive a new daily activity goal at the beginning of each day. Participants will use their Fitbit activity trackers to track their “active minutes” (AM), which are equivalent to moderate-to-vigorous physical activity minutes. At the beginning of the program, participants will receive a daily AM goal of 10- 20 AM per day based on their baseline level of activity during the run-in period. After the first program week or day (for weekly and daily adaptive, respectively), AM goal adaptations will be driven by an algorithm that sets the new goal as the 4th highest day of AM (55th percentile) in the prior 9 days.^{39,54}

Decision Points. Participants in this trial will be randomly assigned to fixed timing or adaptive timing. Fixed timing runs from a schedule that specifies the exact time (1-2 times per day) that the decision rules are run, though the times vary each day. In adaptive timing, the decision rules run hourly and participant data determines when the message should be sent (limited to 1-2 per day, mirroring the fixed schedule). In adaptive timing, messages can be delivered in closer proximity to when a behavior is completed (< 1 hour; to immediately reinforce goal achievement), or, if their usual behavior patterns suggest that receiving the message at the current time would not be ideal, the decision rules can continue to run and send a more appropriate message later in the day (e.g., not sending an activity reminder message at 9am if the participant does not usually exercise until after 7pm). This is done with additional variables in the adaptive timing decision rules that take into account participants' usual behavioral patterns.

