Aim 2 Analysis. In Aim 2 we will conduct mediation analyses to test the relationships between the intervention components and hypothesized mediators, thus refining the underlying conceptual model. In contrast to mediation analyses conducted on data from an RCT, we will be able to fit models specifying which intervention component is mediated by each hypothesized mediator. For example, while we hypothesize that autonomy will mediate the relationship between the intervention component, message choice, and weight, it is possible that other mediators—e.g., relatedness—will explain this relationship. It is also possible that autonomy will mediate the relationship between other intervention components (e.g., decision points for message timing) and weight. This step will provide important information for improving our understanding of how the intervention components work and for revising our conceptual model. Mediators to be tested include the proximal theoretical

mediators of component effects (self-regulation, competence, relatedness, relevance, and autonomy) and the more distal behavioral mediators (daily self-weighing, dietary intake, and physical activity). We will test the mediation effects for significance using the general approach described in MacKinnon.

Aim 3 Exploratory Analyses. In Aim 3 we will conduct moderation analyses to test differential response to intervention components. The primary moderator to be tested is intervention engagement, which will include percentage of messages viewed, number of days of diet self-monitoring, number of days of physical activity tracking, number of days of self-weighing, and lessons viewed. Exploratory moderators will include gender, race and ethnicity, and initial BMI status. Results will provide important information for future research aimed at developing mobile interventions tailored and optimized for differing levels of engagement and subgroup membership.

Handling Missing Data

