6. DATA COLLECTION AND MANAGEMENT

The rigorous system used for participant tracking, data collection, management, and quality control procedures for our previous projects (SNAP: U01HL090864; IMPACT: R01CA204965) will be modified for this study. All data will be entered using the REDCap computer-assisted program that has built-in validation checks for range, data type, and completeness. All measurements will undergo consistency and outlier checks, compared with raw data, and edited as required. REDCap includes detailed audit logs that document any database changes, and we will document protocols for cleaning data.

Participants will provide physical data (objective weight and self-reported height), self-reported questionnaire data online, and self-reported physical activity data over the telephone specifically for research purposes. All self-report online data will be collected using secure REDCap surveys. A subset of participants local to the UNC clinic will have objective height and weight data taken in the clinic in order to validate home scale weights. Food log data from the study smartphone application will be transmitted to study servers, and weight and activity data from Fitbit be will transmitted to study servers. Identifiable information collected in online surveys will include the participant's name, address, phone numbers, and date of birth.

Risk to privacy and/or confidentiality

We expect a breach of confidentiality to be rare or infrequent. Most communication during the study period will take place via telephone, direct emails, text messages, or through the smartphone app—either to deliver questions, conduct assessments, or remind participants to complete questionnaires. We do not anticipate any risks of harm as a result of these communications; however, there is always a possibility that their scale data, tracker data, or activity in the app will be intercepted.

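### Aim 2 tests two behavioral pathways weakly: activity is listed as a mediator by self-report only, although tracker minutes are collected daily, and diet after randomization is measured only together with the 6-month weight

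*Combined protocol and SAP*

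**What the plan says.** Section 4 (Aim 2 Analysis) names "the more distal behavioral mediators (daily self-weighing, dietary intake, and physical activity" as the behavioral mediators. It gives no instrument, time window or temporal order for any of them, and only cites a general method for testing mediated effects.

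The instruments come from section 3 (Measures), under the heading "Other Anthropometric and Key Behavioral Mediators (collected at baseline, 3 months, and 6 months". For activity the text is "Physical activity will be assessed with the Paffenbarger Physical Activity Questionnaire (PAQ", which covers leisure-time activity. Section 6 confirms the mode: "self-reported physical activity data over the telephone specifically for research purposes". For diet the entry is "Dietary Intake (Baseline, 6 months", with two 24-hour recalls at each time. The Data Collection paragraph of section 3, however, limits the 3-month contact to psychosocial measures and medical events.

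Section 2 (Adaptive Activity Goals) says that all participants use a tracker to record active minutes, "which are equivalent to moderate-to-vigorous physical activity minutes". The first goal is set "based on their baseline level of activity during the run-in period", and later goals are computed from the preceding nine days of active minutes. Sections 2 and 6 say that these data go to the study servers. Under Process and Adherence Measures, the research quantity defined from the tracker is wear: "the study will collect data on the number of days the Fitbit was worn". Self-weighing is taken from the smart scale over the whole 6 months.

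**The concern.** The activity-goal factor sets goals in tracker active minutes, weekly or daily. If its effect on weight runs through activity, those minutes are the first place to look. The listed mediator is a different quantity, recalled leisure-time activity, and probably a noisier one. Participants are told their assignment (section 7, Recruitment), so errors in self-report may also differ by level. A real activity pathway could then be missed.

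For diet, the only value after randomization is taken when the weight change that it is meant to explain has already happened. Weight already lost can change what people eat or report at month 6. An apparent mediated effect could run from weight to diet.

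Aim 2 is a stated secondary objective, meant to revise the conceptual model. A false null for activity or a reversed diet result would mislead that revision.

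**Working it through.** **1. Mediators side by side**

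| Quantity | Measure | Times after randomization | Value before the 6-month weight? |
|---|---|---|---|
| Self-weighing | smart scale, days weighed | throughout | yes |
| Activity, listed mediator | PAQ self-report | 3 and 6 months by the heading; not at 3 months by the Data Collection paragraph | unclear |
| Activity, tracker minutes | collected, no mediator role | daily | yes |
| Diet | two 24-hour recalls | 6 months | no |

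The daily food logs do not fill the diet gap for the diet factor, because one level logs calories and the other logs red foods.

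**2. The plan's own sample size.** Section 4 assumes a 1 kg effect, SD 4 kg, 5% error (taken as two-sided) and 80% power. The standard two-group formula gives 252 per level, 504 in total; the exact t-test gives power 0.8006 at 505. For attrition, 505/0.83 = 608.4, and 19 × 32 = 608. The plan's figures reproduce. They concern main effects on weight; no power is given for mediation. I use N = 505 below.

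**3. Activity: what random error in the mediator does.** Assumed, not from the documents: component effect on true activity d = 0.3 SD, activity-weight correlation r = 0.3 in absolute value, reliability ρ. Joint significance needs both paths:

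- component to mediator: Φ(d√ρ·√505/2 − 1.96), with √505/2 = 11.24
- mediator to weight: Φ(atanh(r√ρ)·√501 − 1.96), with √501 = 22.38

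| ρ | first path | second path | product |
|---|---|---|---|
| 0.3 | 0.455 | 0.960 | 0.44 |
| 0.4 | 0.568 | 0.990 | 0.56 |
| 0.5 | 0.664 | 0.998 | 0.66 |
| 0.6 | 0.742 | 1.000 | 0.74 |
| 0.7 | 0.805 | 1.000 | 0.80 |
| 0.8 | 0.854 | 1.000 | 0.85 |

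Simulations of the same set-up agree within about 3 points: 43-44%, 55-58%, 65-68%, 74-77%, 80-82% and 85-86%. The estimated indirect effect shrinks in proportion to ρ: of a true 0.3 × 0.3 = 0.09, about 30-50% remains at ρ = 0.3-0.5 and 70-80% at ρ = 0.7-0.8.

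The result moves with d. At 0.2 SD, the same formulas give only 47-52% at ρ = 0.7-0.8. At 0.4 SD, they already give 66-89% at ρ = 0.3-0.5.

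**4. Diet: two recalls, taken with the endpoint.** With an assumed single-day intraclass correlation of 0.2 to 0.5, the reliability of two recalls is 2·ICC/(1 + ICC): 0.4/1.2 = 0.33 up to 1.0/1.5 = 0.67.

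For direction, assume no mediation at all, a 0.25 SD component effect on weight, and weight driving month-6 intake with correlation g. The spurious indirect effect is (0.25g)·g, a share g² of the total effect. In 4,000 simulated trials per value:

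| g | mediator-weight path significant | both paths significant | spurious share g² |
|---|---|---|---|
| 0.1 | 62% | 3% | 1% |
| 0.2 | 99% | 9% | 4% |
| 0.3 | 100% | 13% | 9% |
| 0.5 | 100% | 29% | 25% |

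**5. What an earlier window can and cannot do.** Suppose instead that the mediator is taken over weeks 1-12 and is driven by early weight change (correlation 0.1, 0.2 or 0.3), and that 3- and 6-month weight correlate 0.8 (assumed). With no mediation, the mediator-weight path is still significant in 45%, 95% and 100% of simulated trials, and both paths in 3%, 8% and 13%. An earlier window gives order relative to the endpoint, but does not exclude reverse causation from early weight loss.

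**The case against.** A reader might infer that the behavioral mediation question goes unanswered, or that the plan rules the tracker out. The documents support neither. Self-weighing is objective and continuous. Activity and diet both have baseline values, so change can be analyzed. Aim 2 names no instrument, so tracker minutes are unassigned rather than excluded.

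The PAQ also has a stated rationale: it belongs to a common core set of obesity measures, it yields minutes of moderate-to-vigorous activity, and section 3 says that its changes have predicted weight change. If the section heading is right, it is also taken at 3 months, ahead of the endpoint. Tracker minutes have a weakness that the PAQ lacks: they are missing on non-wear days, and wear may depend on engagement or component level. The 500-step rule was written to count days worn, not to validate active minutes. Nor is the run-in placed relative to randomization; the pre-randomization steps in section 7 do not mention it.

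The power contrast depends on giving the questionnaire a low reliability and the device a high one. At 0.6 against 0.7 it nearly disappears (74-77% against about 80%).

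Most of this stands. It argues for adding the tracker measure rather than replacing the PAQ, and for not presenting any power gain as established. It does not explain why the quantity on which one factor directly acts has no assigned role, and it does not give diet a value before the endpoint.

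**Conclusion.** The point holds as a limitation of two of the three behavioral pathways in a secondary aim. Activity is weakly tested if only the PAQ is used, most clearly for the activity-goal factor. For diet, an association can be estimated but its direction is not identified. The size is conditional: power is roughly 43-68% at reliability 0.3-0.5, 74-77% at 0.6 and 80-86% at 0.7-0.8, for an assumed 0.3 SD component effect and 0.3 correlation. The documents give no reliability for either instrument. Possible bias in self-report from known assignment is plausible but not quantified. Component selection rests on weight and 5% weight loss, and is unaffected.

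**What to change.** In section 3 (Measures) and section 4 (Aim 2 Analysis):

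- State instrument, time window and temporal order for each mediator.
- Add mean daily tracker active minutes on valid wear days, run-in value against weeks 1-12, as the main activity mediator, at least for the activity-goal factor. Report the PAQ alongside it.
- Define a valid day (the existing 500-step rule is a starting point), compare wear by component level, and add a sensitivity analysis for non-wear.
- Confirm that the run-in precedes randomization.
- Reconcile the heading and the Data Collection paragraph on whether the PAQ is collected at 3 months.
- Use mediator values from before the endpoint where they exist, and state that these do not exclude reverse causation from early weight loss.
- Report the 6-month diet result as a concurrent, exploratory association, not as evidence of mediation.

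The cost is wording and analysis time; the tracker data already reach the study servers. The downsides are informative missingness on non-wear days and a weaker diet claim.

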4. STATISTICAL CONSIDERATIONS

Sample Size and Power

We defined a 1-kg weight change as more than a minimal effect of any given component on overall weight loss. We estimated standard deviation based on a prior cell phone-delivered intervention for YAs that found a standard deviation of 6.9 kg for a weight change difference of 2.2 kg between groups;⁹ therefore, we conservatively estimated a standard deviation of 4 times our 1-kg weight change estimate. Assuming a type 1 error rate of 5% and a standard deviation of 4 kg, reaching 80% power would require 505 total participants. Assuming a 17% attrition rate at 6 months based on our previous studies with YAs and rounding up to a whole number per condition results in a total of 608 participants needed. Thus, each of the two levels of each component will have 304 randomly assigned participants, with 19 participants in each of the 32 conditions.

Statistical Analysis

Aim 1 Analysis. To test for differences in weight change across time by the five intervention components, we will use mixed effects models on an intention-to-treat data set, with effects modeled as component \times time interactions and the 6-month outcome as the primary endpoint. We will run separate models for (a) mean weight change and (b) the proportion of participants achieving 5% weight loss, the latter constituting a second-level decision-making criterion in cases where effects for mean weight change are equal. All higher-order interactions between components will also be modeled (e.g., adaptive physical activity goals \times message choice \times time interaction). The ability to test all higher-order interactions between intervention components, without reducing power, is a key advantage of the factorial experiment, as this is not possible in a traditional multi-component RCT. We will be using effect (-1,1) coding rather than dummy (0,1) coding, which keeps any covariances among main effects and interactions to a minimum. Once we have identified important effects in the initial set of models, we will establish parsimonious prediction models in which coefficients that do not contribute significantly to mean weight loss (or proportion achieving 5% weight loss) will be set to zero.

Aim 2 Analysis. In Aim 2 we will conduct mediation analyses to test the relationships between the intervention components and hypothesized mediators, thus refining the underlying conceptual model. In contrast to mediation analyses conducted on data from an RCT, we will be able to fit models specifying which intervention component is mediated by each hypothesized mediator. For example, while we hypothesize that autonomy will mediate the relationship between the intervention component, message choice, and weight, it is possible that other mediators—e.g., relatedness—will explain this relationship. It is also possible that autonomy will mediate the relationship between other intervention components (e.g., decision points for message timing) and weight. This step will provide important information for improving our understanding of how the intervention components work and for revising our conceptual model. Mediators to be tested include the proximal theoretical

mediators of component effects (self-regulation, competence, relatedness, relevance, and autonomy) and the more distal behavioral mediators (daily self-weighing, dietary intake, and physical activity). We will test the mediation effects for significance using the general approach described in MacKinnon.

Aim 3 Exploratory Analyses. In Aim 3 we will conduct moderation analyses to test differential response to intervention components. The primary moderator to be tested is intervention engagement, which will include percentage of messages viewed, number of days of diet self-monitoring, number of days of physical activity tracking, number of days of self-weighing, and lessons viewed. Exploratory moderators will include gender, race and ethnicity, and initial BMI status. Results will provide important information for future research aimed at developing mobile interventions tailored and optimized for differing levels of engagement and subgroup membership.

Handling Missing Data

While every effort will be made to avoid missing data with proper tracking efforts, we do expect some missing data due to attrition and nonresponse. Under the MAR assumption, we will use the suite of multiple imputation tools in Stata (v.15 or greater) to (1) conduct a detailed analysis of the missing data, beginning with an examination of the number and proportion of missing values among the variables of interest; (2) identify potential auxiliary variables that are either correlated with a missing variable/(s) or are believed to be associated with missingness; (3) use MI IMPUTE, with at least 20 imputations, to derive the imputed data set; (4) rerun analyses on the imputed data set; and (5) verify the stability of MAR inference by conducting sensitivity analyses which modify the imputation step to accommodate potentially nonignorable missing-data mechanisms. This process will be followed separately for each estimation model (i.e., mean weight change from baseline to 6 months, proportion achieving 5% weight loss).

Strengths and Limitations.

One limitation is the potential for contamination, as YAs may be connected to others via social media and learn about the study from common sources. This is mitigated by the fact that the intervention components of interest are uniquely tailored to individuals and the intervention is delivered via individual smartphones. Although participants will be limited to those with smartphone and internet access, prevalence of smartphone use is highest among young adults (96% of 18-29-year-olds, 92% of 30-49-year-olds), and the app will be available to iPhone and Android users, thereby extending generalizability. While our study requires extensive programming, our preliminary work, in which we have created complex algorithms and decision rules for multiple libraries of intervention messages (400+ for Nudge pilot, 1000+ for IMPACT study tailored feedback), demonstrates our ability to create infrastructure and content for this project. Our proposal has several strengths that outweigh its limitations. It targets an understudied population of YAs at risk for weight gain. Our work advances the science of JITAI development—answering key questions about adaptation and tailoring—and is guided by a conceptual model, which will further our understanding of how JITAI components and mobile interventions may operate via key theoretical mediators. We use ADOPT Core Measures to enable collaboration, data pooling, and identification of predictors of heterogeneity in treatment response. Moreover, our delivery via a smartphone app increases potential for widespread reach and adoption around the country. Our study builds upon our prior work focused on YAs and will be one of the first to systematically optimize a fully automated remotely delivered JITAI. Our work will elucidate appropriate and feasible mobile intervention strategies among YAs and holds promise for promoting weight loss among YAs that may decrease their risks for morbidity and mortality.

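### The sample size rests on an SD of 4 kg described as conservative, but the only SD the plan cites is 6.9 kg, at which the stated 80% power for a 1-kg effect is about 37%

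*Combined protocol and SAP*

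**What the plan says.** Section 4 (Statistical Considerations, Sample Size and Power) sets the target effect: "We defined a 1-kg weight change as more than a minimal effect of any given component on overall weight loss". For variability it turns to one prior phone-delivered trial in young adults, which "found a standard deviation of 6.9 kg for a weight change difference of 2.2 kg between groups". From this it concludes: "therefore, we conservatively estimated a standard deviation of 4 times our 1-kg weight change estimate". The calculation follows: with a 5% type 1 error rate and a "standard deviation of 4 kg, reaching 80% power would require 505 total participants". Attrition of 17% then brings the total to 608, that is 304 per level of each component and 19 in each of 32 conditions.

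The plan gives no other source for 4 kg. It claims no variance reduction from covariates or repeated measures, and it shows no power at any other SD.

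Two other statements depend on this one. Aim 1 (Study Objectives) says the design is powered for main effects and for all two-way interactions. The Aim 1 Analysis says that coefficients without a significant contribution will be set to zero when the prediction models are built.

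**The concern.** The only empirical SD in the document is 6.9 kg, and the calculation does not use it. The plan transfers a ratio instead: SD divided by the observed difference. It enlarges that ratio from 3.14 to 4 and multiplies it by its own 1-kg target. This treats the SD as proportional to the effect one hopes to detect. The SD of weight change describes how much people differ from one another, and targeting 1 kg instead of 2.2 kg does not change it. With the cited SD, a 1-kg effect is a standardised effect of 1/6.9 = 0.145, not 1/4 = 0.25.

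Significance is the selection rule, and the retained components form the intervention that goes on to a separate randomised trial. If power is far below 80%, components with an effect the plan itself regards as more than minimal are likely to be discarded. Those that survive will tend to have overestimated effects.

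**Working it through.** **Inputs (all from Section 4).** Difference between the two levels of a component: 1 kg. SD used: 4 kg. SD cited: 6.9 kg. Type 1 error 5%. Power 80%. Evaluable N: 505. Attrition 17%. Randomised N: 608. The plan does not state whether the test is two-sided. Two-sided is inferred because a one-sided test would need 396 and does not reproduce 505.

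**Formula.** With equal allocation, the standard error of a main effect, expressed as the difference between levels, is SE = 2·SD/√N. The N for 80% power is about 4·SD²·(1.960 + 0.842)²/1².

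**Reproducing the plan.** At SD 4: 4 × 16 × 7.849 = 502.3, or 252 per level (504 in total). The noncentral t gives exactly 505, whether the model has 2 or 32 parameters. For attrition, 505/0.83 = 608.4, and 608 = 32 × 19. The 1 kg must therefore be the difference between levels. Read as a coefficient under (-1, 1) coding it would be a 2-kg difference, which needs only 126 participants at SD 4.

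**Changing only the SD.** Power is for a 1-kg effect by noncentral t. The detectable effect is 2.80·SE and the half-width is 1.96·SE, both at N = 505.

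| SD (kg) | SE (kg) | Power, N = 505 | Power, N = 608 (no attrition) | Detectable at 80% (kg) | 95% CI half-width (kg) |
|---|---|---|---|---|---|
| 4.0 | 0.356 | 80% | 87% | 1.00 | 0.70 |
| 5.0 | 0.445 | 61% | 69% | 1.25 | 0.87 |
| 5.5 | 0.490 | 53% | 61% | 1.37 | 0.96 |
| 6.0 | 0.534 | 46% | 54% | 1.50 | 1.05 |
| 6.9 | 0.614 | 37% | 43% | 1.72 | 1.20 |

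**N that 80% power would need at SD 6.9.** The noncentral t gives 1,497 evaluable. Then 1,497/0.83 = 1,804 enrolled, or 1,824 at a whole 57 per condition. This shows the size of the gap and is not a proposal.

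**Effect on selection.** If all five components truly give 1 kg, the expected number found significant is 5 × 0.80 = 4.0 at SD 4 and 5 × 0.369 = 1.8 at SD 6.9. At SD 6.9 an estimate must exceed about 1.20 kg to be significant, so a true 1-kg component that survives is estimated on average at about 1.6 kg: 1 + 0.614 × (0.378/0.370), the mean of a normal estimate above that cut-off. Power falls below 50%, so that most such components are missed, once 1.96 × 2·SD/√505 exceeds 1, that is at an SD above about 5.7 kg.

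**Interactions.** Under effect coding, a two-way interaction contrast of the same size has the same SE, so Aim 1's claim for interactions is affected equally.

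**The case against.** **The claim of conservatism has a coherent reading.** The multiplier 4 exceeds the source ratio of 3.14, so the assumed standardised effect (0.25) is smaller than the source's (2.2/6.9 = 0.32). That is true on the standardised scale. But the target was also cut from 2.2 kg to 1 kg, and the margin makes up only a small part of that cut.

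**The 6.9 kg may not be the right quantity.** The plan does not say whether it is a within-arm SD of change, or at what follow-up it was measured. This stands as a limit on the 37%. It does not support 4 kg: if 6.9 kg does not apply, 4 kg has no documented basis at all. Any SD from 5 to 6.9 kg leaves power at 61% or less with 505 evaluable.

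**The analysis may be more efficient than a comparison of completers.** Mixed models, multiple imputation with auxiliary variables and frequent smart-scale weights could recover some information. If all 608 contributed fully, power at 6.9 kg would be 43%. Reducing a residual SD from 6.9 to 4 kg would require explaining 1 - (4/6.9)² = 66% of the variance of weight change, and the plan claims no such gain. It is also unclear that a 3-month assessment weight will exist: Section 3 (Study Procedures) says weight is measured at all time points, but restricts the 3-month collection to psychosocial measures and medical events.

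**The arithmetic itself is right, and no estimate is biased by the sample-size assumption.** The first part is correct: the fault lies in the input. The second holds for the full set of estimates, but not for those that remain after selection on significance.

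**Conclusion.** The concern holds. The step from 6.9 kg to 4 kg is invalid, and calling the result conservative is wrong on the scale that determines power. At the plan's own cited SD, 505 evaluable participants give 37% power for a 1-kg component effect, against the stated 80%, and the effect detectable with 80% power is 1.72 kg.

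These figures assume two-sided 5% testing (inferred), 505 evaluable, no variance reduction from the model, and 6.9 kg taken at face value as the plan takes it. The direction does not depend on the exact SD: any value above 4 kg puts power below 80% at 505 evaluable. Whether most true 1-kg components would be lost does depend on it, because that requires an SD above about 5.7 kg. The correction is needed because the overstated power feeds a significance-based selection rule for the primary aim.

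**What to change.** 1. In Sample Size and Power, delete the word *conservatively* and the derivation of the SD from the target effect. State instead that 608 enrolled and 505 evaluable give 80% power for 1.0 kg if the SD is 4 kg, but 37% for 1.0 kg (80% for 1.72 kg) at the cited 6.9 kg. Include a table over SD 4 to 6.9 kg. If there are 6-month weight-change data that support 4 kg, cite them.
2. Qualify the Aim 1 statement on power for main effects and two-way interactions in the same way.
3. Re-estimate the pooled SD of weight change from accrued data without using component assignment, and restate the detectable effect. Ignoring assignment inflates the SD only slightly: five 1-kg main effects add 5 × 0.5² = 1.25 kg² to the variance, which takes 4.0 to √17.25 = 4.15 kg.
4. In the Aim 1 Analysis, report the estimate and confidence interval for every component, and state that a coefficient set to zero is not evidence of no effect.

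The cost is protocol and SAP wording, a short blinded calculation and a less favourable stated power. Enrolment and data collection do not change.
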